3.2 Exclusion Criteria

- 3.21 Patients who have had chemotherapy or radiation \leq 2 weeks of registration.
- 3.22 For Cohort 1 only: Patients with evidence of Intermediate 2 or High risk disease (according to DIPSS, see Appendix VI).
- 3.23 For Cohort 1 only: Patients with a bone marrow biopsy with $<15\%$ cellularity, evidence of collagen fibrosis, osteosclerosis, or blasts $> 10\%$ in peripheral blood or marrow (demonstrating advanced disease).
- 3.24 Patients who have received a prior stem cell transplant
- 3.25 Patients who have received radiation to the spleen within 3 months prior to registration
- 3.26 Patients with intolerance to compounds similar to pegylated interferon alpha-2b.
- 3.27 Patients with evidence of \geq grade 2 peripheral sensory neuropathy.
- 3.28 Any of the following, because this study involves an investigational agent whose genotoxic, mutagenic and teratogenic effects on the developing fetus and newborn are unknown:
 - Pregnant women
 - Nursing women
 - Men or women of childbearing potential who are unwilling to employ adequate contraception
- 3.29a Co-morbid systemic illnesses or other severe concurrent disease which, in the judgment of the investigator, would make the patient inappropriate for entry into this study or interfere significantly with the proper assessment of safety and toxicity of the prescribed regimens.
- 3.29b Immunocompromised patients or patients known to be HIV positive and currently receiving antiretroviral therapy.
- 3.29c Uncontrolled simultaneous illness including, but not limited to, ongoing or active infection, symptomatic congestive heart failure, unstable angina pectoris, cardiac

arrhythmia, history of depression, or psychiatric illness/social situations that would limit compliance with study requirements.

- 3.29d Receiving any other investigational agent which would be considered as a treatment for the primary neoplasm.
- 3.29e History of myocardial infarction \leq 6 months prior to registration, or congestive heart failure requiring use of ongoing maintenance therapy for life-threatening ventricular arrhythmias.
- 3.29f History of significant or major fundoscopic findings including, but not limited to, retinal exudates, hemorrhage, detachment, neovascularization, papilloedema, optic atrophy, micro-aneurysm or macular changes.
- 3.29g Other active malignancy at time of registration. EXCEPTIONS: Non-melanotic skin cancer or carcinoma-in-situ of the cervix.

4.0 Test Schedule

Cycle = 28 days

Parameter	Prior to Registration ≤14 days	Active Monitoring					
		Cycle 1 Day 1	Cycle 1 Days 8, 15, 22 ±2 days	Cycle 2 and Cycle 3 Day 15	Prior to Treatment Cycle 2 Day 1 and Beyond	Prior to Treatment Cycles 2, 3, 6, 9 & 12 and every 3 cycles thereafter Day 1 ±3 days	At Treatment Discontinuation ±7 days
Medical History	X						
Prior Diagnosis/Prior Treatment	X						
Height (pre-study only)	X						
Weight, ECOG PS	X					X	X
Physical Examination	X					X	X
Serum pregnancy test(HCG) ³	X						
Vital Signs	X	X ⁷				X	X
CBC with Differential and peripheral blood smear (Can be from home lab for interval monitoring)	X		X ⁷	X ⁷	X ²		X
Chemistries (Sodium, potassium, creatinine, chloride, SGOT (AST), SGPT (ALT), Alkaline Phosphatase, Total bilirubin, glucose)	X		X ⁷	X ⁷	X ²		X
JAK2, BCR-ABL, CALR, & MPL	X ⁶					X ⁶	
Treatment Evaluation (see Section 11)						X	X
EKG	X						
Transfusion Assessment	X				X ⁵	X	X
Symptom Assessment Package (Patient Questionnaire Booklet)	X					X ¹	X

Parameter	Prior to Registration	Active Monitoring					
	≤ 14 days	Cycle 1 Day 1	Cycle 1 Days 8, 15, 22 ± 2 days	Cycle 2 and Cycle 3 Day 15	Prior to Treatment Cycle 2 Day 1 and Beyond	Prior to Treatment Cycles 2, 3, 6, 9 & 12 and every 3 cycles thereafter Day 1 ± 3 days	At Treatment Discon- tinuation ± 7 days
Clinical measurement of spleen and liver by physical exam	X					X	X
Research Blood Samples		X ⁷			X ^{7,8}		
Adverse Event monitoring	X	X ⁷	X ⁷		X ^{5,7}	X	X
Bone marrow biopsy and aspirate including cytogenetics ⁴	X					X	

Footnotes:

1. To be completed prior to treatment on Day 1. Patient questionnaire booklet must be used; copies are not acceptable for this submission.
2. To be completed on Day 1 of Cycles 4, 5, 7, 8, 10 and 11 at local MD office and faxed to study team
3. Pregnancy test must be completed ≤ 7 days prior to registration
4. ≤ 90 days prior to registration. Repeat at cycle 6 and 12 only.
5. Patients can be contacted by telephone for adverse event assessment when not seen in the clinic.
6. Must be completed at least 90 days prior to registration. Any positive results at baseline will be repeated again every three cycles (Cycle 3, 6, 9, etc).
7. Must be completed prior to treatment.
8. Research blood samples only collected on C1D1, C2D1, and C3D1 prior to treatment.

5.0 Grouping Factor:

Cohort: Cohort 1 (early stage MF) versus Cohort 2 (intermediate-2 or high risk MF)

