9.0 Ancillary Treatment/Supportive Care

- 9.1 Antiemetics may be used at the discretion of the attending physician.
- 9.2 Blood products and growth factors should be utilized as clinically warranted and following institutional policies and recommendations. The use of growth factors should follow published guidelines of the American Society of Clinical Oncology (42) Update of Recommendations for the Use of Hematopoietic Colony-Stimulating Factors: Evidence-Based, Clinical Practice Guidelines. J Clin Oncol 18(20): 3558-3585, 2000.
- 9.3 Patients should receive full supportive care while on this study. This includes blood product support, antibiotic treatment, and treatment of other newly diagnosed or concurrent medical conditions. All blood products and concomitant medications such as antidiarrheals, analgesics, and/or antiemetics received from the first day of study treatment administration until 30 days after the final dose will be recorded in the medical records.

9.4 Diarrhea: This could be managed conservatively with loperamide. The recommended dose of loperamide is 4 mg at first onset, followed by 2 mg every 2-4 hours until diarrhea free (maximum 16 mg/day).

In the event of grade 3 or 4 diarrhea, the following supportive measures are allowed: hydration, octreotide, and antidiarrheals.

If diarrhea is severe (requiring intravenous rehydration) and/or associated with fever or severe neutropenia (grade 3 or 4), broad-spectrum antibiotics must be prescribed.

Patients with severe diarrhea or any diarrhea associated with severe nausea or vomiting **should be hospitalized** for intravenous hydration and correction of electrolyte imbalances.

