- 6) Important Medical Events (IME) that may not result in death, be life threatening, or require hospitalization may be considered serious when, based upon medical judgment, they may jeopardize the patient or subject and may require medical or surgical intervention to prevent one of the outcomes listed in this definition. (FDA, 21 CFR 312.32; ICH E2A and ICH E6).

ALL SERIOUS adverse events that meet the above criteria MUST be immediately reported to the sponsor within the timeframes detailed in the table below using the AdEERS Multiple Agent Template

Hospitalization	Grade 1 Timeframes	Grade 2 Timeframes	Grade 3 Timeframes	Grade 4 & 5 Timeframes
Resulting in Hospitalization ≥ 24 hrs		7 Calendar Days		24-Hour 3 Calendar Days
Not resulting in Hospitalization ≥ 24 hrs	Not required		7 Calendar Days	

NOTE: Protocol specific exceptions to expedited reporting of serious adverse events are found in section 10.31 of the protocol.

Expedited AE reporting timelines are defined as:

- “24-Hour; 3 Calendar Days” - The AE must initially be reported via paper Adverse Event Expedited Report – Single Agent or Multiple Agents within 24 hours of learning of the AE, followed by a complete expedited report within 3 calendar days of the initial 24-hour report.³
- “7 Calendar Days” - A complete expedited report on the AE must be submitted within 7 calendar days of learning of the AE.³

Serious adverse events that occur more than 30 days after the last administration of investigational agent/intervention and have an attribution of possible, probable, or definite require reporting as follows:

Expedited 24-hour notification followed by complete report within 3 calendar days for:

- All Grade 4, and Grade 5 AEs

Expedited 7 calendar day reports for:

- Grade 2 adverse events resulting in hospitalization or prolongation of hospitalization
- Grade 3 adverse events

Effective Date: May 5, 2011

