13.0 Treatment/Follow-up Decision at Evaluation of Patient

- 13.1 Patients who are without progression will continue treatment per protocol.
- 13.2 Patients who develop PD while receiving therapy will go to the event-monitoring phase.
- 13.3 Patients who go off protocol treatment for reasons other than PD will go to the event-monitoring phase per Section 18.0.
- 13.4 A patient is deemed *ineligible* if after registration, it is determined that at the time of registration, the patient did not satisfy each and every eligibility criteria for study entry. The patient will go directly to the event-monitoring phase of the study (or off study, if applicable).
 - If the patient received treatment, all data up until the point of confirmation of ineligibility must be submitted. Event monitoring will be required per Section 18.0 of the protocol.
 - If the patient never received treatment, on-study material and the end of active treatment/cancel notification form must be submitted. No further data submission is necessary.
- 13.5 A patient is deemed a *major violation*, if protocol requirements regarding treatment in cycle 1 of the initial therapy are severely violated that evaluability for primary end point is questionable. All data up until the point of confirmation of a major violation must be submitted. The patient will go directly to the event-monitoring phase of the study. Event monitoring will be required per Section 18.0 of the protocol.
- 13.6 A patient is deemed a *cancel* if he/she is removed from the study for any reason before any study treatment is given. On-study material and the End of Active Treatment/Cancel Notification Form must be submitted. No further data submission is necessary.

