15.15 Pharmacokinetic information: Mean P1101 serum concentration time curves were comparable across treatment groups and reached a peak at approximately 3 to 5 days after dosing and then declined gradually, with elimination half-lives of 60 to 118 hours. Single dose pharmacokinetic parameters (Cmax, AUC and AUC0-t) for P1101 increased with dose. The results of the power model analysis of dose proportionality for P1101 suggested more than proportional kinetics with increasing dose, as the slopes of the power model ranged from 1.19 to 1.36. The lack of dose proportionality for P1101 in this study may be attributed partly due to the high intersubject pharmacokinetic variability, and the small number of subjects.

15.16 Potential Drug Interactions: No information available.

15.17 Known potential toxicities: Adverse events reported most frequently (>10% of subjects) in either treatment in the *single dose* study include injection site erythema, headache, myalgia, decreased neutrophil count, back pain, increased body temperature, decreased white blood cell count, arthralgia, chills, fatigue, eye pain, feeling cold, nausea, increased alanine aminotransferase, somnolence, upper respiratory tract infection, feeling hot, decreased appetite, and pyrexia.

Adverse events reported in the *repeated dose* study have so far been mild to moderate. These include anemia, dizziness, dry mouth, dry skin, dyspnea, ear pain, epigastralgia, epistaxis, fatigue, fidget, flank pain, headache, myalgia, pruritus, respiratory distress, skin allergy, skin erythema, somnolence, sore throat, UTI, WBC decrease.

Investigators should also be informed of published data on marketed pegylated interferon. Subjects receiving *repeated doses* of interferon α -2b, have reported adverse events that include influenza-like symptoms, fever, headache, fatigue, rigors, musculoskeletal pain, arthralgia, back pain, injection site disorders (bruising, itching, and irritation), dry mouth, nausea/vomiting, diarrhea, abdominal pain, anorexia, weight, dizziness, impaired concentration, impaired memory, depression, anxiety/emotional lability/irritability, insomnia, alopecia, pruritus, dermatitis, rash, increased sweating, dyspnea, cough, and hypothyroidism. Common laboratory adverse events include neutropenia,

thrombocytopenia, increases in triglycerides and total cholesterol, abnormalities indicative of altered thyroid and liver function. Ten to fifteen percent of patients develop antibodies to interferon.

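### No adverse-event contact is scheduled after the discontinuation visit, which is not tied to the last dose, so late non-fatal events have no scheduled active ascertainment in the documents shown

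*Combined protocol and SAP*

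**What the plan says.** Section 4.0 ends with the column "At Treatment Discontinuation ±7 days". The row "Adverse Event monitoring" is marked at baseline, during treatment and in that last column, and not after it. The blood count and chemistry rows end there too. Footnote 5 allows telephone assessment ("Patients can be contacted by telephone for adverse event assessment when not seen in the clinic"), but it is attached to an on-treatment column and not to any contact after treatment.

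After that visit, Section 13.3 says: "Patients who go off protocol treatment for reasons other than PD will go to the event-monitoring phase per Section 18.0". Section 13.2 sends patients with progression the same way. The follow-up table in Section 18.0 lists a single event-monitoring form. It is due every 3 months until progression or further treatment, at progression, every 6 months afterwards, at death and at a new primary, up to 3 years after registration. The adverse-event form appears only in the table for the active-monitoring phase.

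Several rules reach past the visit:

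- Section 9.3 requires blood products and concomitant medications "received from the first day of study treatment administration until 30 days after the final dose will be recorded" in the medical records.
- Sections 10.312 and 10.5231 require reporting of any death within 30 days, whatever the attribution.
- Section 10.4 has a separate rule for "Serious adverse events that occur more than 30 days after the last administration of investigational agent/intervention", which keeps those at least possibly related reportable.
- Section 10.53 refers late adverse events to a Forms Packet that is not part of the documents.

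Section 15.15 says that serum concentration "reached a peak at approximately 3 to 5 days after dosing", with "elimination half-lives of 60 to 118 hours".

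**The concern.** The adverse-event profile and tolerability are the two secondary objectives (2.21, 2.22). Section 16.322 summarises each patient's maximum grade per event type and states no end to the observation period. If drug is still present after the last scheduled check, an event that first appears or worsens in the following weeks enters those tables only through unscheduled reporting. Section 15.17 lists depression and other psychiatric events for the class, which a patient may not mention unasked. After day 1 of cycle 3 a local doctor may see the patient between visits (7.5), so the study team may not learn of late events by chance.

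With at most 6 patients in cohort 1 and 13 in cohort 2 for Stage 1, a single event alters a reported rate noticeably. Section 9.3 also sets a 30-day recording duty that no scheduled contact serves.

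**Working it through.** The plan states no washout or exposure duration, so there is no figure of its own to reproduce. The check applies first-order elimination to its inputs.

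**Inputs.** Time to peak 3 to 5 days and half-life 60 to 118 hours (15.15). Dosing on Days 1 and 15 of a 28-day cycle, or on Day 1 only at dose level -2 (4.0, 7.1). Day 1 holds, with the study chair contacted if they exceed 28 days (Table 8.2). A 30-day horizon (9.3, 10.312, 10.5231). The five-half-life rule is an assumption: 0.5^5 = 0.031, so about 3% of peak is left.

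**Length of the exposure tail** = time to peak + 5 × half-life / 24, in days after the last dose:

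- 60 h: 3 + 12.5 = 15.5, or 5 + 12.5 = 17.5.
- 118 h: 3 + 24.6 = 27.6, or 5 + 24.6 = 29.6.

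With 4 to 7 half-lives instead of 5, the ranges are 13.0 to 22.5 days (60 h) and 22.7 to 39.4 days (118 h).

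**Fraction of peak left on day t** = 0.5^((t − time to peak) × 24 / half-life). For example, on day 7 with peak at day 3 and 60 h: 0.5^(96/60) = 0.33. With peak at day 5 and 118 h: 0.5^(48/118) = 0.75.

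| Day after last dose | Half-life 60 h | Half-life 118 h |
|---|---|---|
| 7 | 33–57% | 57–75% |
| 14 | 5–8% | 21–28% |
| 21 | about 1% | 8–10% |
| 30 | 0.1% or less | 2–3% |

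**Days without a scheduled check, out of 30** = 30 − day of the visit, or 0 if the visit is later. The plan does not fix the day of the visit relative to the last dose, so these are scenarios:

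- Visit on day 7: 30 − 7 = 23 days.
- Visit when the next two-weekly dose is due: 30 − 14 = 16 days.
- Visit when the next dose is due at dose level -2: 30 − 28 = 2 days.
- Stop after a 28-day hold that began on Day 1, 14 days after a Day 15 dose: 14 + 28 = 42 days after the last dose. Even 7 days early this is day 35, so there is no gap.

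**Direction of any error.** A maximum taken over a shorter period cannot exceed the maximum over a longer one. Missed late events can therefore only lower the tabulated grades. They do so only when a new event type, or a new worst grade, first occurs after the visit. The documents give no rate for such events, so the size cannot be calculated.

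**The case against.** The strongest reply is that the plan never sets a 30-day window for non-fatal adverse events. Section 9.3 concerns medications and transfusions, 10.312 and 10.5231 concern deaths, and 10.4 changes the attribution rule for serious events after day 30. Sections 10.521 and 10.522, which govern Grade 2 to 4 events, carry no time limit. This stands. The 30 days serve here as a horizon taken from neighbouring rules, not as an adverse-event window that the plan breaches.

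A reader might also infer three stronger claims that the documents do not support:

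- *Late events are not looked for, or surface only if volunteered.* Deaths, progression and new primaries are followed. Serious events must be reported at once whether or not related, and related ones stay reportable beyond 30 days. The Forms Packet named in 10.53 and the content of the event-monitoring form cannot be seen.
- *Patients who stop for toxicity are observed for the shortest time.* Table 8.2 requires weekly rechecks during Day 1 holds, so a patient who stops after such a hold has had repeated checks off drug.
- *Every patient has a 23-day gap.* That needs a visit on day 7. With two-weekly dosing the decision to stop may come when the next dose is due, or later.

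The exposure bound of 29.6 days likewise needs the longest half-life and the latest peak. Half-lives alone give 12.5 to 24.6 days.

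These replies narrow the point but do not remove it. Rules for submitting a known event do not create an occasion on which someone asks, and the documents shown contain none after discontinuation.

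**Conclusion.** The point holds in limited form. In the documents shown, non-fatal adverse events after the discontinuation visit have no scheduled active ascertainment, and the visit is not anchored to the last dose. Exposure plausibly lasts about 15.5 to 29.6 days after that dose, given first-order decay and the five-half-life convention. The unobserved part of a 30-day horizon runs from none to about 23 days, depending on when the visit falls. It could affect up to 19 patients in Stage 1, though not all to the same degree.

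Any effect on the 16.322 tables is toward under-reporting, and its size is unknown. A demonstrated bias would be too strong a reading. The conclusion also depends on the unseen Forms Packet: if it already prescribes a timed contact after the last dose, what remains is to bring that contact into the protocol. This is a worthwhile, inexpensive improvement to safety data, and it does not undermine the design.

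**What to change.** - **Section 4.0:** add one column, 30 days (+7) after last dose, for assessment of adverse events, concomitant medications and transfusions. Allow it by telephone when the patient is not seen in clinic, and include review of any local laboratory results already available.
- **Section 18.0:** add an adverse-event form for this contact to the follow-up table.
- **Sections 13.2 and 13.3:** start event monitoring after this contact.
- **Section 16.322:** state that the adverse-event tables include events through this contact.

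The cost is at most 19 calls in Stage 1 (13 in cohort 2 plus 6 in cohort 1) and a short amendment. The limit is that a call finds symptoms and results that already exist. It will not detect a silent fall in blood counts or a rise in liver enzymes that nobody has tested for. The change does not affect dosing or the efficacy decision rules.

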2.3 Exploratory and Correlative Research

2.31 To evaluate quality of life (QOL) and patient-reported symptoms using the MPN-SAF with P1101 for patients with myelofibrosis. (Emanuel et al. J Clin Oncol. 2012) by cohort (early vs intermediate-2/high risk)

2.32 To evaluate the impact of P1101 on bone marrow and histological features of myelofibrosis including cytogenetics, blast percentage, fibrosis, and JAK2-V617F allele burden by cohort (early vs intermediate-2/high risk)

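### Footnote 6 of the test schedule sets a minimum age of 90 days, and no maximum, for the baseline mutation test; this conflicts with the row's own 14-day heading and should be a maximum age.

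*Combined protocol and SAP*

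**What the plan says.** The Section 4.0 row "JAK2, BCR-ABL, CALR, & MPL" is marked in the pre-registration column, headed "Prior to Registration ≤14 days", and again in the on-treatment column. Both marks carry footnote 6, which sets the baseline timing: "Must be completed at least 90 days prior to registration". It then sets the repeat rule: "Any positive results at baseline will be repeated again every three cycles (Cycle 3, 6, 9, etc".

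Two other footnotes set pre-registration windows, and both set a maximum age. Footnote 3 reads "Pregnancy test must be completed ≤ 7 days prior to registration". Footnote 4, on the marrow, reads "≤ 90 days prior to registration. Repeat at cycle 6 and 12 only".

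Section 6.7 requires pretreatment tests to follow the windows in the schedule. Section 6.6 allows treatment to start up to 14 days after registration. Objective 2.32, which is exploratory, includes the effect of P1101 on "JAK2-V617F allele burden by cohort".

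**The concern.** Taken at its word, footnote 6 rejects recent mutation tests and accepts old ones of any age. That is the reverse of what a baseline window is for.

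This row is the only mutation baseline that the protocol schedules. No mutation test is listed for Cycle 1 Day 1, the research samples in Section 14.1 are banked serum, and Section 17.0 lists no tissue specimens. Any comparison of on-treatment JAK2-V617F burden with baseline therefore rests on this test. The repeat rule also depends on it, because a marker that was negative on the old test is not followed.

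An old baseline leaves room for change that is not due to P1101. Cohort 2 may include patients who failed ruxolitinib (3.13), and 3.21 asks for only about two weeks free of chemotherapy or radiation. A test 90 or more days old can therefore precede or overlap other treatment.

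**Working it through.** No sample size, power or error rate enters this point, and the plan gives no figure to reproduce. The check compares date windows.

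Let *d* be the days from the mutation test to registration, and *g* the days from registration to first dose. The age of the baseline at first dose is *d* + *g*.

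**Inputs**

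| Source | Condition |
|---|---|
| 4.0, footnote 6 (mutation panel) | *d* ≥ 90, no upper limit |
| 4.0, heading of the column holding the same test | *d* ≤ 14 |
| 4.0, footnote 4 (marrow) | ≤ 90 days |
| 4.0, footnote 3 (pregnancy test) | ≤ 7 days |
| 6.6 | 0 ≤ *g* ≤ 14 |
| 4.0 | cycle = 28 days |

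**As written**

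1. Footnote 6 and the column heading together need *d* ≥ 90 and *d* ≤ 14. No date qualifies.
2. The marrow row sits in the same 14-day column and has its own 90-day window, so the schedule does let a footnote replace the heading. If footnote 6 does so, every test with *d* = 0 to 89 fails.
3. The minimum age at first dose is then 90 + 0 = 90 days when treatment starts on the day of registration, and 90 + 14 = 104 days when it starts on the last permitted day. At registration the minimum is 90/28 = 3.2 cycles. There is no maximum.
4. Set against the marrow window, the only shared date is *d* = 90 exactly. A mutation test and a marrow done on the same day could both comply only on that day.

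**With footnote 6 as a maximum (*d* ≤ 90)**

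5. The permitted range is *d* = 0 to 90, and the age at first dose is 0 + 0 = 0 to 90 + 14 = 104 days.
6. Tests done in the 14-day screening period become acceptable, and the window matches that for the marrow.

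Nothing else in the documents restates or corrects the limit. Section 18.1 asks for the mutation form within two weeks of registration, but that is a deadline for a form and not a window for the test.

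**The case against.** The strongest reply is that this is a slip of the pen. Beside a 14-day heading and two footnotes that set maximum ages, most sites would take footnote 6 to mean within 90 days, and their baselines would be sound. That reply stands as regards the likely harm. It does not remove the point, because the written rule is binding under 6.7: a site that follows it turns away a recent test, and a site that follows the apparent intent departs from the schedule.

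A second reply is that little depends on this test, and that is largely right. Objective 2.32 is exploratory, Section 16.33 gives no analysis of allele burden, and the row does not say that the JAK2 assay is quantitative. The notes to Table 11.1 say molecular response is not needed for CR, and it is not among the criteria listed for PR or CI.

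A reader might infer three stronger things that the documents do not support:

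- **That every patient will have an outdated baseline.** This assumes that all sites apply the literal wording.
- **That a fixed majority of at least 62% of the interval from baseline test to first repeat lies before registration.** That figure is 90/(90 + 56) = 90/146 for a repeat at Cycle 3 Day 1, with treatment starting on the day of registration. With the 14-day start allowed by 6.6 it is 90/(90 + 14 + 56) = 90/160 = 56%, so 62% is not a lower bound. A corrected limit of 90 days or fewer would still allow a test at day 90, so the share does not measure the defect. Nor is it a bias, since the documents give no rate of change for allele burden.
- **That newly diagnosed Cohort 1 patients would be shut out.** The timing of this test is not an eligibility criterion in 3.1 or 3.2, and 13.4 defines ineligibility by those criteria. Missing the window breaches 6.7, but the documents do not say that it bars the patient. They also give no times since diagnosis.

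**Conclusion.** The inconsistency is real and uncorrected. Footnote 6 cannot be met together with its own column heading, and it runs opposite to footnotes 3 and 4. Read literally with 6.7, it excludes tests from days 0 to 89 and leaves the only scheduled mutation baseline at least 90 days old at first dose, with no upper limit.

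The expected consequence is modest: baselines of uneven age for one exploratory objective, some doubt over which markers should be followed, and deviations that need not occur. The size of any distortion in allele-burden change cannot be given from the documents. The primary endpoint and the Cohort 2 decision rule are untouched.

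Two readings underlie this. That the footnote replaces the heading is taken from how the marrow row works. That a maximum of 90 days was intended is an inference, strongly supported by footnote 4 but not stated anywhere.

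**What to change.** Reword footnote 6 so that the mutation test is done 90 days or fewer before registration, as footnote 4 does for the marrow, and state that this overrides the 14-day heading for this row. The repeat rule can stay as it is.

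This changes an assessment window only, in one footnote. The cost is a repeat of a routine test in the few patients whose only result is older than 90 days. The change does not guarantee a fresh baseline, but it puts a ceiling on its age where there is none now.
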